## 5.6 Treatment of Nivolumab Related Infusion Reactions

Since nivolumab contains only human immunoglobulin protein sequences, it is unlikely to be immunogenic and induce infusion or hypersensitivity reactions. However, if such a reaction were to occur, it might manifest with fever, chills, rigors, headache, rash, pruritis, arthralgias, hypo- or hypertension, bronchospasm, or other symptoms. All Grade 3 or 4 infusion reactions should be reported as an SAE if criteria are met. Infusion reactions should be graded according to NCI CTCAE (v4.03) guidelines. Treatment recommendations are provided below and may be modified based on local treatment standards and guidelines as appropriate:

**For Grade 1 symptoms:** (Mild reaction; infusion interruption not indicated; intervention not indicated): Remain at bedside and monitor subject until recovery from symptoms. The following prophylactic premedications are recommended for future infusions: diphenhydramine 50 mg (or equivalent) and/or paracetamol 325 to 1000 mg (acetaminophen) at least 30 minutes before additional nivolumab administrations.

**For Grade 2 symptoms:** (Moderate reaction requires therapy or infusion interruption but responds promptly to symptomatic treatment [eg, antihistamines, non-steroidal anti inflammatory drugs, narcotics, corticosteroids, bronchodilators, IV fluids]; prophylactic medications indicated for 24 hours): Stop the nivolumab infusion, begin an IV infusion of normal saline, and treat the

subject with diphenhydramine 50 mg IV (or equivalent) and/or paracetamol 325 to 1000 mg (acetaminophen); remain at bedside and monitor subject until resolution of symptoms. Corticosteroid or bronchodilator therapy may also be administered as appropriate. If the infusion is interrupted, then restart the infusion at 50% of the original infusion rate when symptoms resolve; if no further complications ensue after 30 minutes, the rate may be increased to 100% of the original infusion rate. Monitor subject closely. If symptoms recur then no further nivolumab will be administered at that visit. Administer diphenhydramine 50 mg IV, and remain at bedside and monitor the subject until resolution of symptoms. The amount of study drug infused must be recorded on the electronic case report form (eCRF). The following prophylactic premedications are recommended for future infusions: diphenhydramine 50 mg (or equivalent) and/or paracetamol 325 to 1000 mg (acetaminophen) should be administered at least 30 minutes before additional nivolumab administrations. If necessary, corticosteroids (recommended dose: up to 25 mg of IV hydrocortisone or equivalent) may be used.

**For Grade 3 or Grade 4 symptoms:** (Severe reaction, Grade 3: prolonged [ie, not rapidly responsive to symptomatic medication and/or brief interruption of infusion]; recurrence of symptoms following initial improvement; hospitalization indicated for other clinical sequelae [eg, renal impairment, pulmonary infiltrates]). Grade 4: (life threatening; pressor or ventilatory support indicated): Immediately discontinue infusion of nivolumab. Begin an IV infusion of normal saline, and treat the subject as follows. Recommend bronchodilators, epinephrine 0.2 to 1 mg of a 1:1,000 solution for subcutaneous administration or 0.1 to 0.25 mg of a 1:10,000 solution injected slowly for IV administration, and/or diphenhydramine 50 mg IV with methylprednisolone 100 mg IV (or equivalent), as needed. Subject should be monitored until the investigator is comfortable that the symptoms will not recur. Nivolumab will be permanently discontinued. Investigators should follow their institutional guidelines for the treatment of anaphylaxis. Remain at bedside and monitor subject until recovery from symptoms. In the case of late-occurring hypersensitivity symptoms (eg, appearance of a localized or generalized pruritis within 1 week after treatment), symptomatic treatment may be given (eg, oral antihistamine, or corticosteroids).

### 5.3 Concomitant Therapy

Supportive measures consistent with optimal patient care may be given throughout the study. Concomitant medications will be captured in the medical record and will not be recorded on the case report form.

- Therapies considered necessary for the patient's well-being may be administered at the discretion of the investigator. These therapies include, but are not limited to antibiotics, analgesics, antihistamines, or other medications. Guidance for growth factors and transfusions of red blood cells, platelets, or fresh frozen plasma are described below:
- Packed red blood cells (RBCs): Transfusions of 2 units of packed RBCs should be considered for a decline in hemoglobin to <8 g/dl or symptoms of cardiovascular compromise. The following transfusion thresholds and guidelines are recommended for study participants:
  - hemoglobin <8 g/dl, 2 units of packed RBCs; hemoglobin <7, three units of packed RBCs

- Platelets: Six to 10 units of random donor platelets or one cytopheresis unit of single donor platelets should be administered to all subjects with signs of hemostatic failure (i.e., bleeding or petechiae) or life-threatening thrombocytopenia (i.e., platelet count < 10,000/ $\mu$  L)
- Growth factor use with epoetin, darbepoetin, or granulocyte colony-stimulating factor must be terminated at least 14 days before initiation of study treatment and may not be used as part of supportive therapy while the patient is on study, except if in patients best interest after approval of PI (e.g., neutropenic fever)
- Patients should not receive androgens or steroids for treatment of their anemia or thrombocytopenia as part of supportive therapy
  - Patients may receive hydrocortisone prophylactically to prevent transfusion reactions but chronic systemic steroid ( $\geq$ 10 mg/day prednisone) are not allowed.
- Over-the-counter herbal preparations or dietary supplements, are not allowed throughout the trial. Patients should stop using these herbal medications at least 7 days prior to the first dose of study medication.

#### **5.4 Correlative studies**

Tumor tissue, blood samples and bone marrow aspirate will be collected on a separate IRB approved laboratory protocol (PA13-0291) for immune monitoring as previously published, under the supervision of the Immunotherapy Platform. Participation in this protocol is optional. In bone marrow biopsies immunohistochemical studies will be performed to evaluate disease and immunological cell markers such as CD4 and CD8 T cells. In peripheral blood, we will also evaluate malignant and immune cell populations including but not limited to CD4 and CD8 T cells in pre and post therapy samples.

Peripheral blood will be collected under an IRB-approved laboratory protocol for testing of biomarkers described in this clinical protocol at the following time points:

- At screening: 20cc
- Prior to each dose of study drug 20cc
- At progression/discontinuation of protocol participation 20cc

#### **5.5 Pretreatment Evaluation**

- History and physical exam including vital signs, body weight and height, and spleen and liver measurements. This also includes a transfusion history for 3 months prior to day 1 and concomitant medication notation (within 7 days of study day 1)
- CBC and differential, electrolytes (Na, K, Cl, HCO3), creatinine, uric acid, BUN, glucose, total and direct bilirubin, and amylase, lipase, SGPT and SGOT, PT/PTT, INR (within 7 days of study day 1).
- Bone marrow biopsy and aspirate (within 1 month of study day 1, or within 3 months of study day 1 if patient was not on any therapy).
- Pregnancy test (for FCBP only) within 24 hours of study day 1
- Myeloproliferative Neoplasm - Symptom Assessment Form Total Symptom Score (MPN-SAF TSS) questionnaire (within 7 days of study day 1).

## 5.6 Evaluation During Study

- Directed history and physical examination including vital signs, body weight, and spleen and liver measurements on Days 1, 7, and 14 of Cycle 1, then on Day 1 and Day 14 (+/- 2 days) of Cycles 2 – 4, then on Day 1 of Cycle 5, and then on Day 1 (+/- 7 days) of every 3rd cycle after that (Cycles 8, 11, 14 and so on). This also includes a transfusion history and concomitant medication notation.
- CBC and differential, electrolytes (Na, K, Cl, HCO3), creatinine, BUN, glucose, total bilirubin, SGOT and SGPT, amylase and lipase on Days 1, 7, and 14 of Cycle 1, then on Day 1 and Day 14 of Cycles 2 – 4 (+/- 2 days), then on Day 1 of Cycle 5, and then on Day 1 (+/- 7 days) of every 3rd cycle after that (Cycles 8, 11, 14 and so on).
- Bone marrow aspiration and biopsy after 4 cycles, and if deemed appropriate by the investigator, then every 12 weeks.
- Response assessment after 4 cycles of therapy, then every 12 weeks
- Pregnancy test after 2 and 4 cycles of therapy, then every 12 weeks
- Continuous assessment of AEs
- MPN-SAF TSS questionnaire on Day 1 and Day 14 (+/- 2 days), of cycles 1-4, then on Day 1 of Cycle 5 (+/- 7 days), then Day 1 (+/- 7 days) of every 3rd cycle after that.

Every effort will be made to adhere to the schedule of events and all protocol requirements. Variations in schedule of events and other protocol requirements that do not affect the rights and safety of the patient will not be considered as deviations. Such variations may include laboratory and history and physical exam assessments completed outside of schedule, occasional missed required research samples.

The patient will be contacted by the PI and his staff approximately 30, 60 and 100 days after discontinuation of study drug to assess for AE's, unless the patient receives further MF-directed treatment. Pregnancy test (for FCBP only) will be required approximately 30, 60 and 100 days after discontinuation of study drug.

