### **5.4 Management Algorithms**

Immuno-oncology (I-O) agents are associated with AEs that can differ in severity and duration than AEs caused by other therapeutic classes. Nivolumab is considered an immuno-oncology agent in this protocol. Early recognition and management of AEs associated with immuno-oncology agents may mitigate severe toxicity. Management algorithms have been developed to assist investigators in assessing and managing the following groups of AEs: Gastrointestinal, Renal, Pulmonary, Hepatic, Endocrinopathies, Skin, Neurological.

For subjects expected to require more than 4 weeks of corticosteroids or other immunosuppressants to manage an AE, consider recommendations provided in the algorithms. These algorithms are found in Appendix G of this protocol. The guidance provided in these algorithms should not replace the Investigator's medical judgment but should complement it.

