§See above for definitions of anemia response, spleen response, and progressive disease. Increase in severity of anemia constitutes the occurrence of new transfusion dependency or a ≥20 g/L decrease in hemoglobin level from pretreatment baseline that lasts for at least 12 weeks. Increase in severity of thrombocytopenia or neutropenia is defined as a 2-grade decline, from pretreatment baseline, in platelet count or absolute neutrophil count, according to the Common Terminology Criteria for Adverse Events (CTCAE) version 4.0. In addition, assignment to CI requires a minimum platelet count of ≥25 000 × 10(9)/L and absolute neutrophil count of ≥0.5 × 10(9)/L.

¶Applicable only to patients with baseline hemoglobin of <100 g/L. In patients not meeting the strict criteria for transfusion dependency at the time of study enrollment (see as follows), but have received transfusions within the previous month, the pretransfusion hemoglobin level should be used as the baseline.

¶Transfusion dependency before study enrollment is defined as transfusions of at least 6 units of packed red blood cells (PRBC), in the 12 weeks prior to study enrollment, for a hemoglobin level of <85 g/L, in the absence of bleeding or treatment-induced anemia. In addition, the most recent transfusion episode must have occurred in the 28 days prior to study enrollment. Response in transfusion-dependent patients requires absence of any PRBC transfusions during any consecutive “rolling” 12-week interval during the treatment phase, capped by a hemoglobin level of ≥85 g/L.

#In splenectomized patients, palpable hepatomegaly is substituted with the same measurement strategy.

††Symptoms are evaluated by the MPN-SAF TSS. The MPN-SAF TSS is assessed by the patients themselves and this includes fatigue, concentration, early satiety, inactivity, night sweats, itching, bone pain, abdominal discomfort, weight loss, and fevers. Scoring is from 0 (absent/as good as it can be) to 10 (worst imaginable/as bad as it can be) for each item. The MPN-SAF TSS is the summation of all the individual scores (0-100 scale). Symptoms response requires ≥50% reduction in the MPN-SAF TSS.

‡‡Baseline values for physical examination refer to pretreatment baseline and not to post treatment measurements.

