## **9.0 STATISTICAL CONSIDERATIONS**

This is a single-center phase II trial to determine the efficacy of nivolumab as a monotherapy in subjects with Primary, Post Polycythemia Vera, or Post Essential Thrombocythemia Myelofibrosis (PMF, post-PV MF, or post-ET MF). The primary endpoint is the objective response rate (ORR) after 8 doses of therapy (4 cycles), defined as CR (complete remission) + PR (partial remission) + CI (clinical improvement). Responses will be categorized according to the revised International Working Group-Myeloproliferative Neoplasms Research and Treatment (IWG-MRT) and European LeukemiaNet (ELN) consensus criteria for myelofibrosis.

An optimum two-stage design proposed by Simon will be implemented. We assume a target ORR of 35%, and a response rate of 18% or lower will be considered not desirable. With a type I error rate of 7% and 80% power, we will enroll 16 patients in the first stage. If 3 or fewer patients achieve a response the trial will be stopped. If 4 or more out of the first 16 patients have a response, accrual will continue until a total of 40 patients have been enrolled. After the first 16 patients have enrolled, the study will not enroll new patient until enough responses (at least 4 responses out of 16 patients) are observed to warrant the continuation of the study. At the end of the study, if 11 or more out of these 40 patients achieve a response, the treatment of nivolumab will be considered efficacious and worth further investigation. Under this Simon's Optimum two-stage design, the probability of early termination is 68% if the true ORR is 18% and the expected sample size is 23.7 patients. Patients will be enrolled from MDACC and patients will be registered through the Clinical Oncology Research System (CORE). The estimated accrual rate is 1-2 patients per month. An interim analysis (response summary) will be submitted to the IND Monitor following the treatment of 16 and 40 patients.

The method of Thall, Simon and Estey will be used for toxicity monitoring for this study. Toxicity will be monitored among the 40 patients. Denote the probability of toxicity by  $p(T)$ ,

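### Endocrinopathies are a named risk group, but no thyroid function test is scheduled before or during treatment

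*Combined protocol and SAP*

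**What the plan says.** - **Named risk.** Section 5.4 (Management Algorithms) states: "Management algorithms have been developed to assist investigators in assessing and managing the following groups of AEs: Gastrointestinal, Renal, Pulmonary, Hepatic, Endocrinopathies, Skin, Neurological". It adds that recognising and managing such events early may limit severe toxicity, and section 5.2 (Dose Delay Criteria) makes a similar point. Of the algorithms it says: "These algorithms are found in Appendix G of this protocol". That appendix is not in the text available for review.
- **Pretreatment panel.** Section 5.5 (Pretreatment Evaluation) lists CBC with differential, electrolytes, "creatinine, uric acid, BUN, glucose, total and direct bilirubin, and amylase, lipase, SGPT and SGOT, PT/PTT, INR".
- **On-study panel.** Section 5.6 (Evaluation During Study) lists CBC with differential, electrolytes, "creatinine, BUN, glucose, total bilirubin, SGOT and SGPT, amylase and lipase on Days 1, 7, and 14 of Cycle 1". The panel is repeated on Days 1 and 14 of Cycles 2 to 4, on Day 1 of Cycle 5, and then at every third cycle.
- **Other detection.** The same section schedules directed history and examination, with vital signs and body weight, and "Continuous assessment of AEs".
- **Rules that use a baseline.** Section 5.3 (Criteria to Resume Treatment) refers to a drug-related event returning to Grade 1 or lower or to its baseline value. Section 7.1 has pretreatment events recorded as baseline events and captured again if they worsen.
- **Symptom score.** The footnote to the section 6.0 response criteria says of the patient-reported MPN-SAF TSS that "this includes fatigue, concentration, early satiety, inactivity, night sweats, itching, bone pain, abdominal discomfort, weight loss, and fevers".

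**The concern.** The scheduled chemistry follows the renal group (creatinine, BUN) and the hepatic group (bilirubin, transaminases). It also follows pancreatic enzymes, although the pancreas is not a named group. For endocrinopathies it offers only glucose and electrolytes. No thyroid test appears anywhere in the supplied text.

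A site that follows the schedule therefore has no pretreatment thyroid value and tests later only on clinical suspicion. Suspicion may be slow to arise. Fatigue, poor concentration, inactivity and night sweats are symptoms that these patients already score as part of their disease, and they can also come from thyroid dysfunction. That overlap is general clinical knowledge, not a figure from the documents. Patients who benefit may be treated for 4 years, and after Cycle 5 the scheduled visits fall to every third cycle.

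Three things are at stake:

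- timely recognition of a risk that the protocol itself names;
- the ability to tell a new abnormality from one present at entry;
- to a lesser degree, the symptom component of the primary endpoint.

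**Working it through.** **Step 1. Named groups against scheduled laboratory markers**

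| Group in section 5.4 | Scheduled laboratory marker |
|---|---|
| Renal | creatinine, BUN |
| Hepatic | bilirubin, SGOT, SGPT |
| Endocrinopathies | glucose and electrolytes only |
| Gastrointestinal, pulmonary, skin, neurological | no dedicated marker |

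**Step 2. What a missing baseline affects**

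The resume rule in section 5.3 and the baseline-event rule in section 7.1 both need a pretreatment state for comparison. For thyroid function there is none. Exclusion 6 screens out autoimmune disease by history, and section 2.1 notes that autoimmune phenomena occur in MF, so unrecognised disease at entry is possible.

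Attribution also decides what is recorded. Section 7.1 captures events at least possibly related to treatment, but captures unrelated or unlikely-related events only from Grade 3 upward. A Grade 1 or 2 thyroid event wrongly judged to pre-date treatment could therefore be left out of the safety tables.

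**Step 3. The route to the primary endpoint**

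Section 9.0 counts CR, PR and CI after 8 doses. Under section 6.0, CI can be met by a symptoms response alone, which is a fall of at least 50% in the TSS. No rule covers a score raised by something other than MF. A route to the ORR therefore exists.

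**Step 4. Scale of that route**

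First, the plan's own design. With X1 the responders among the first 16 and X2 those among the next 24:

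- early termination = P(X1 ≤ 3);
- power = sum over x from 4 to 16 of P(X1 = x) × P(X2 ≥ 11 − x);
- expected N = 16 + (1 − early termination) × 24.

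At ORR 18%, early termination is 0.678 (stated 68%), expected N is 16 + 0.3223 × 24 = 23.7 (stated 23.7), and type I error is 0.073 (stated 7%). At ORR 35%, power is 0.802 (stated 80%). The design is reproduced to rounding.

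Next, two assumptions that the documents do not supply. Let m be the share of patients with thyroid dysfunction that is not found, and s the share of responders who respond by symptoms only. Suppose the dysfunction masks every such response. Then:

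- ORR = 0.35 × (1 − m × s);
- expected lost responders = n × 0.35 × m × s.

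| m | s | ORR | Power | Lost of 40 | Lost of 16 |
|---|---|---|---|---|---|
| 0 | any | 35.0% | 80.2% | 0 | 0 |
| 5% | 25% | 34.6% | 78.8% | 0.18 | 0.07 |
| 10% | 25% | 34.1% | 77.3% | 0.35 | 0.14 |
| 10% | 50% | 33.3% | 74.2% | 0.70 | 0.28 |
| 15% | 50% | 32.4% | 70.8% | 1.05 | 0.42 |
| 15% | 100% | 29.8% | 59.2% | 2.10 | 0.84 |

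For example, 40 × 0.35 × 0.10 × 0.50 = 0.70. The range of 5% to 15% means 2 to 6 affected patients among 40, but only a fraction of them would be lost responders.

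**The case against.** The strongest reply has four parts.

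- **A named group does not imply a routine test.** Gastrointestinal, pulmonary, skin and neurological events are also named and have no dedicated laboratory marker. That is true, so the case cannot rest on the list alone. It rests on two further facts: a blood test can be added to draws already planned, and the symptoms that would prompt clinical suspicion overlap with those of MF.
- **Clinical detection remains.** A reader might infer that thyroid dysfunction would simply go undetected. The documents do not support that. History, vital signs, weight and adverse-event review are scheduled throughout, with contacts about 30, 60 and 100 days after treatment stops. Appendix G may also call for a thyroid work-up on suspicion. What is missing is scheduled and baseline testing.
- **Attribution is not impossible.** Section 7.2 has the investigator assign attribution for every event. A missing baseline weakens that judgement without preventing it.
- **The endpoint argument is thin.** A reader might infer that, with thresholds of 4 of 16 and 11 of 40, a few affected patients could decide the trial. An affected patient is lost only if that patient would have responded, by symptoms alone, and the dysfunction blocked the 50% fall. Losing about two responders needs 15% affected and every responder symptoms-only. New dysfunction hides responses, so it cannot manufacture a success. An upward error is conceivable if disease present at entry is treated later, but nothing in the documents sizes it. The endpoint is also read after 4 cycles, so the 4-year exposure bears on safety and not on the ORR.

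These replies limit the point but do not remove it. None of them supplies a pretreatment value or a scheduled test.

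**Conclusion.** The gap is real and is mainly one of safety monitoring. The protocol names endocrinopathies, asks for early recognition, and schedules no thyroid function test before or during treatment. The consequences are slower recognition, weaker attribution, and rules on baseline values that have no thyroid value to refer to.

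An effect on the ORR is possible but unquantified. In the illustrative cases with up to 10% affected and up to half of responders symptoms-only, the expected loss is 0.18 to 0.70 responders among 40, and power stays at 74.2% or more. The fall to 59.2% needs the extreme combination. The main direction is conservative. These figures rest on assumed values of m and s and on complete masking, so they show scale only.

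The documents do not support reading this as a material threat to the primary endpoint. The change is worth making on safety grounds alone.

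**What to change.** Add TSH, with reflex free T4 if abnormal, to the laboratory list in section 5.5 (Pretreatment Evaluation). Add it periodically to the list in section 5.6 (Evaluation During Study), at visits where blood is already drawn. The documents give no basis for a particular interval, so the sponsor should choose which of those visits. Management stays with the Appendix G algorithm, and no dosing, delay or discontinuation rule changes.

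The cost is one assay on existing draws, with no extra visit, procedure or staff, and no change to the sample size. The downside is a small laboratory charge and some incidental mild abnormalities to record.

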## **5.0 TREATMENT PLAN**

On this study 4 weeks of therapy is considered one cycle of therapy. Nivolumab will be given IV in outpatient setting at 3 mg/kg approximately every 2 weeks (every 14 days +/- 2 days; patients may be dosed no less than 12 days from the previous dose of drug) for 8 doses followed by a maintenance regimen of one dose every 12 weeks. Nivolumab should be administered as an IV infusion over 60 minutes through an intravenous line containing a sterile, nonpyrogenic in-line filter (0.2- to 1.2-micron, low-protein binding polyethersulfone membrane). Patients experiencing clinical benefit will continue therapy for 4 years unless progression of disease or toxicity warranting discontinuation of therapy is observed.

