### **5.2 Dose Delay Criteria**

Because of the potential for clinically meaningful nivolumab-related AEs requiring early recognition and prompt intervention, management algorithms have been developed for suspected AEs of selected categories. Dose delay criteria apply for all drug-related adverse events. Dose delays are also permitted for patient safety (e.g. unrelated medical issues, or life events) at the discretion of the PI.

Nivolumab administration should be delayed for the following:

- Grade 2 pneumonitis
- Grade 2 or 3 colitis
- Aspartate aminotransferase (AST) or alanine aminotransferase (ALT) greater than 3 and up to 5 times upper limit of normal (ULN) or direct bilirubin greater than 1.5 and up to 3 times ULN
- Creatinine greater than 1.5 and up to 6 times ULN or greater than 1.5 times baseline
- Any other severe or Grade 3 treatment-related adverse reactions

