### **5.5 Discontinuation Criteria**

Treatment should be permanently discontinued for the following study drug related events:

- Any life-threatening or Grade 4 adverse reaction
- Grade 3 or 4 pneumonitis
- Grade 4 colitis
- AST or ALT greater than 5 times ULN or direct bilirubin greater than 3 times ULN
- Creatinine greater than 6 times ULN
- Any severe or Grade 3 treatment-related adverse reaction that recurs
- Inability to reduce corticosteroid dose to 10 mg or less of prednisone or equivalent per day within 12 weeks
- Persistent Grade 2 or 3 treatment-related adverse reactions that do not recover to Grade 1 or resolve within 12 weeks after last dose of therapy
- Any dosing interruption lasting > 6 weeks with the following exceptions:
  - Dosing interruptions > 6 weeks but not exceeding 12 weeks to allow for prolonged steroid tapers to manage drug-related adverse events are allowed. Prior to re-initiating treatment in a subject with a dosing interruption lasting > 6 weeks, the Principal Investigator must be consulted. Tumor assessments should continue as per protocol even if dosing is interrupted
  - Dosing interruptions > 6 weeks that occur for non-drug-related reasons may be allowed if approved by the Principal Investigator. Prior to re-initiating treatment in a subject with a dosing interruption lasting > 6 weeks, the Principal Investigator must be consulted. Tumor assessments should continue as per protocol even if dosing is interrupted
- Any adverse event, laboratory abnormality, or intercurrent illness which, in the judgment of the Investigator, presents a substantial clinical risk to the subject with continued nivolumab dosing

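### The hepatic delay and stopping rules are set on direct bilirubin, but the on-study blood panel schedules only total bilirubin

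*Combined protocol and SAP*

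**What the plan says.** Several section numbers are used twice in the protocol, so headings are given here.

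- **Eligibility (Section 4.0).** The bilirubin limit for entry is direct bilirubin no higher than 1.5 times ULN.
- **Dose delay (Section 5.2, Dose Delay Criteria).** One limb of the hepatic rule is AST or ALT above 3 and up to 5 times ULN. The alternative limb is "direct bilirubin greater than 1.5 and up to 3 times ULN".
- **Permanent discontinuation (Section 5.5, Discontinuation Criteria).** For drug-related events the trigger is "AST or ALT greater than 5 times ULN or direct bilirubin greater than 3 times ULN".
- **Before treatment (Section 5.5, Pretreatment Evaluation).** The chemistry list includes "glucose, total and direct bilirubin, and amylase, lipase, SGPT and SGOT".
- **On study (Section 5.6, Evaluation During Study).** The chemistry list includes "creatinine, BUN, glucose, total bilirubin, SGOT and SGPT, amylase and lipase on Days 1, 7, and 14 of Cycle 1". The same list applies at the later visits: Days 1 and 14 of Cycles 2 to 4, Day 1 of Cycle 5, then Day 1 of every third cycle.
- **Dosing (Section 5.0).** Nivolumab is given about every 2 weeks "for 8 doses followed by a maintenance regimen of one dose every 12 weeks".

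The supplied text has no reflex direct bilirubin when total is raised, and no restatement of the thresholds in total bilirubin.

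**The concern.** A numerical dosing rule needs its measurement on the schedule. Here the bilirubin limb of both hepatic rules names an analyte that is measured before treatment and then drops out of the scheduled tests. A site that follows the schedule exactly has no value with which to show that either trigger has been reached.

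The patient at risk has an isolated conjugated rise while total bilirubin, AST and ALT look unremarkable. The rule says to hold or stop the drug, and nothing scheduled shows it. The opposite error is also possible. A site that applies the thresholds to total bilirubin instead could hold doses for a rise that is not conjugated, for example in Gilbert's syndrome, which the eligibility section anticipates. Under Section 5.3 (Criteria to Resume Treatment), a delay beyond 6 weeks generally ends treatment.

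Resumption is affected too. That section asks for return to Grade 1 or below, or to the baseline value. A baseline direct bilirubin exists, but no scheduled follow-up value can be compared with it.

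**Working it through.** The plan states no figure to reproduce. The check compares the analytes named in the rules with those on the schedule, counts the visits affected, and asks how far total bilirubin can stand in for direct.

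**1. Analyte by place in the protocol**

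| Place | Bilirubin analyte |
|---|---|
| Eligibility, Section 4.0 | direct |
| Dose delay, Section 5.2 | direct |
| Discontinuation, Section 5.5 | direct |
| Pretreatment panel, Section 5.5 | total and direct |
| On-study panel, Section 5.6 | total only |

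All three bilirubin limits use direct bilirubin, and the pretreatment list names the two analytes separately. The on-study entry therefore cannot be read as shorthand for both.

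**2. Visits affected**

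Inputs: a cycle is 4 weeks (Section 5.0), and Cycle 1 Day 1 is day 1. Cycle k then starts on day 28 × (k − 1) + 1. Cycle 1 Day 1 is left out of the count, because direct bilirubin is measured within the 7 days before it.

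- Cycle 1: days 7 and 14, giving 2 panels.
- Cycles 2 to 4: days 29, 42, 57, 70, 85 and 98, giving 6 panels.
- Cycle 5 Day 1: day 113, giving 1 panel.
- Total: 2 + 6 + 1 = 9, of which 8 fall within 16 weeks (day 112).
- Later panels at Cycles 8, 11, …, 50 for a patient treated for 52 cycles (52 × 28 = 1,456 days, about 4 years): (50 − 8)/3 + 1 = 15. The count is 16 if Cycle 53 Day 1, day 1,457, is included.
- All panels: 9 + 15 = 24. Direct bilirubin is scheduled in none of them.
- Redosing decisions after dose 1 in the 8-dose phase: 8 − 1 = 7, all within the first window.

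**3. What total bilirubin can and cannot show**

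Direct bilirubin is part of total bilirubin, so direct ≤ total.

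- If total ≤ 1.5 × direct ULN, the delay trigger is excluded. If total ≤ 3 × direct ULN, the stop trigger is excluded.
- If total is above those values, direct may lie on either side of the threshold. No value of total establishes that a trigger has been met.

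**4. Illustration on assumed reference limits**

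The documents give no reference limits. Assume a direct ULN of 0.2 to 0.4 mg/dL and a total ULN of 1.0 to 1.3 mg/dL.

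- Delay trigger: 1.5 × 0.2 = 0.30 to 1.5 × 0.4 = 0.60 mg/dL. This is below the total ULN in every combination.
- Stop trigger: 3 × 0.2 = 0.60 to 3 × 0.4 = 1.20 mg/dL. This is below the total ULN when direct ULN < total ULN / 3, that is, below 1.0/3 = 0.33 mg/dL up to 1.3/3 = 0.43 mg/dL. With a direct ULN of 0.4 it fails when the total ULN is 1.2 or lower.

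On these limits the delay trigger can always be met with a normal total bilirubin, and the stop trigger can be in most combinations. The finding does not rest on this illustration. Steps 1 and 3 are enough.

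**The case against.** The strongest reply is that the residual risk is narrow. AST and ALT are on every panel and form the other limb of the same rules. A raised total bilirubin would be seen, and a clinician could then ask for the direct fraction, since the schedule does not forbid extra tests. Both rules concern drug-related events, so an attribution judgment is needed in any case. The discontinuation list also lets the investigator stop for "Any adverse event, laboratory abnormality, or intercurrent illness which, in the judgment of the Investigator, presents a substantial clinical risk", adverse events are assessed continuously, and other Grade 3 and Grade 4 rules apply. On the assumed reference limits, the direct values that would trigger a delay are small (0.30 to 0.60 mg/dL). The visit counts show how often the assay is absent. They do not measure harm, and the figure of 24 applies only to a patient who stays on treatment for about 4 years.

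Much of this stands. It confines the problem to the bilirubin limb and to cases with little else abnormal, and it means that no number of missed cases can be given. It does not close the gap. The limbs are joined by an *or*, so bilirubin is meant to act alone. Each backstop needs something to prompt it, and a silent conjugated rise may supply nothing.

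One point could not be checked. Section 5.4 (Management Algorithms) says of the organ-specific guidance that "These algorithms are found in Appendix G of this protocol", and that appendix was not among the supplied text. The hepatic algorithm may ask for fractionated bilirubin, but such a step would not put direct bilirubin on the scheduled panel.

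**Conclusion.** The concern holds. As scheduled, the on-study data can sometimes exclude the direct-bilirubin triggers but can never show that one has been met. This covers all 9 panels after Cycle 1 Day 1 through Cycle 5 Day 1, the 7 redosing decisions in that window, and all 24 panels for a patient treated for 52 cycles.

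The conclusion rests on the text of the rules and the schedule, with 28-day cycles. It does not depend on any assumed reference limit. The AST and ALT limbs and the other criteria remain usable. The clinical frequency is unknown, because the documents give no rate for an isolated direct-bilirubin rise. The Simon two-stage design, the response-rate analysis and the toxicity boundaries are unaffected. This is a safety-monitoring inconsistency that should be corrected.

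**What to change.** In the on-study chemistry list of Section 5.6 (Evaluation During Study), replace the total-only entry with "total and direct bilirubin", so that it matches the pretreatment list. Leave the thresholds in Sections 5.2 and 5.5 as they are.

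A reflex direct biliribin when total is raised would be a weaker alternative, because it would miss a conjugated rise within a normal total. Restating the thresholds in total bilirubin would also reconcile the text, but it would change the rules themselves.

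The cost is a wording change and one added assay per panel on blood already drawn. No extra visit or blood draw is needed.
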